8. Patients < 18 years of age
9. Hypersensitivity to any of the following ingredients- sodium chloride, sodium phosphate, calcium chloride and sodium bicarbonate

Trial drug /Interventions:

NeutraSal is a powder that when dissolved in water creates a supersaturated calcium phosphate rinse.

Placebo is a powder consisting of sodium chloride only. Sodium chloride has been chosen as a placebo because it looks like Neutrasal and can be packaged (in foil) like Neutrasal for a double blind effect.

For the study, NeutraSal or placebo will be dispensed by the investigator for the treatment length in a randomized, double-blind procedure. Patients will be provided pre-measured cups, timer to measure length of time patient gargles and patient instructions. Patients will mix product(s) at home in a clean glass or supplied pre-measured cup.

Trial Schedule:

Projected Start Date: July 1st, 2013

Patients with OSAS seen in MUSC (Medical University of South Carolina) sleep clinic who are on CPAP, meet the inclusion criteria and do not have any exclusion criteria, will be invited to participate. After obtaining informed consent, patients will be randomized to the study or placebo groups. The study sponsor, Invado pharmaceuticals will provide a randomization schedule and key. The packets of product and placebo will be numbered 1-32 based on the randomization. Patient 1 will get bag 1, patient 2 will get bag 2 and so on. The study product NeutraSal and placebo will be packed in identical bags. Both the investigators and patients will be blinded to the contents of the bags, hence this will be a double-blind study. Patients will begin taking NeutraSal or placebo at the start of therapy and continue through 12 weeks of treatment.

Patients will receive a baseline visual examination of the oral mucosa in addition to a brief physical exam by the investigators and study coordinator at visit one and receive samples of the product. Patients will be given a diary or questionnaire to record compliance to the product and Xerostomia symptom relief. Patients will be monitored by the principal investigator and the study coordinator via office visit on the baseline visit, visit at 6 weeks and a final visit at 12 weeks.

During these visits the principal investigator and study coordinator will measure the following:

- Xerostomia Questionnaire
- CPAP Compliance measured by objective CPAP downloads as outlined in the follow up visits section

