Patients will complete an oral questionnaire on the state of xerostomia since the initial visit and compliance with CPAP therapy will be reviewed by history and by objective CPAP compliance downloads. Researchers will also review the patient diary for compliance to dosing for medication. CPAP compliance will be recorded as the number of days that the patient used CPAP for ≥ 4 hours/day and the average number of hours of nightly usage. CPAP compliance downloads are provided by durable medical company (DME) providers and usually indicate both of these measures. The dates between which the compliance is measured are also indicated on the compliance downloads provided by the DME providers. CPAP compliance will be recorded on the 2nd visit at 6 weeks and the 3rd visit at 12 weeks. Every effort will be made to obtain CPAP compliance from the date that subjects are started on neurasal/placebo until the dates of the study visits. If CPAP compliance for the entire period of 6 weeks before the 2nd visit and 3 months before the 3rd visit is not available, then any compliance data from a point after subjects received the study drug till a date in the 5-7 week period around visit 2 and in the 10-12 week period around visit 3 will be recorded. The date range of the available compliance data will also be recorded.

If any patients miss follow-up visits, then phone follow-up will be done to obtain information about their product utilization, compliance to dosing and xerostomia symptom relief. CPAP compliance downloads for these patients will be obtained from the DME providers.

Adverse Event Reporting:

Adverse Event (AEs) and Serious Adverse Event (SAEs) will be reported immediately, if suspected to be related to treatment.

Subject Withdrawals:

Subjects will be advised that they are free to withdraw from the study at any time for any reason, or, if necessary, the Investigators may withdraw a subject from the study, according to the following criteria, to protect the subject's health:

- Intolerable adverse effects
- Major violation of study protocol procedures
- Non-compliance with protocol
- Subject unwilling to proceed or consent is withdrawn
- Pregnancy

Statistical Analysis Plan:

This is a double-blind, randomized, intention to treat, controlled clinical trial comparing Neurasal to Sodium Chloride placebo in a 1:1 randomization. The primary analysis is a comparison of CPAP compliance measured by days CPAP was used for ≥ 4 hours per night over 12 weeks.

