The secondary analyses include:

1)CPAP compliance as measured by average number of hours of daily CPAP use.

- 2) improvement in the total score of the Xerostomia questionnaire measured at baseline and 12 weeks.
- 3) Change in resting salivary pH between baseline and 12 weeks.

Statistical analysis will be performed using two sided t-test with $p < 0.1$ being considered significant for this pilot study. Missing data will be treated by use of last data carried forward methodology.

Sample size determination

This is a pilot study in which there are no previous data to determine an accurate sample size that would definitively prove or exclude the possibility of a treatment effect. We estimate the treatment to be effective at improving CPAP compliance in 25% of subjects. This would translate to the same estimated increase in number of days in which CPAP is used for ≥ 4 hours. Therefore, a sample size of 30 subjects is needed to obtain an 80% confidence level with a response rate of 25%. We estimate that 2 subjects will drop out, therefore we will need 32 subjects for this study.

Informed Consent Process:

The language and writing of an informed consent will be at a 6th grade level. No potentially vulnerable subjects will be enrolled in the study, such as, pregnant and lactating women, children, prisoners, cognitively impaired and critically ill subjects.

Privacy and confidentiality:

Human subjects' names will be kept on a password protected database, and will be linked only with a study identification number for this research. There will be no patient identifiers. All data will be entered into a computer and kept on password protected network storage. Hard copies of the records collected as a part of this study will be kept in a locked office. Only the study personnel will have access to the study records.

Risk/Benefit:

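### Last-value-carried-forward also governs the xerostomia-score and salivary-pH endpoints; the distortion is small at the planned dropout but grows with larger or unequal loss, and a better analysis of visits already scheduled is cheap

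*Combined protocol and SAP*

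**What the plan says.** - **Endpoints.** The Statistical Analysis Plan lists, among the secondary analyses, "improvement in the total score of the Xerostomia questionnaire measured at baseline and 12 weeks" and "Change in resting salivary pH between baseline and 12 weeks". No week-6 analysis is named for either.
- **Measurement times.** The Schedule of Study Events marks both the questionnaire and resting pH at baseline, week 6 and week 12. The Trial Schedule section likewise has a "visit at 6 weeks and a final visit at 12 weeks".
- **Test.** A "two sided t-test with $p < 0.1$ being considered significant for this pilot study".
- **Missing data.** "Missing data will be treated by use of last data carried forward methodology". This follows the list of secondary analyses directly. No alternative method or sensitivity analysis appears.
- **Missed visits (Follow Up Visits).** CPAP data have a recovery route: "CPAP compliance downloads for these patients will be obtained from the DME providers". For the rest, "phone follow-up will be done to obtain information about their product utilization, compliance to dosing and xerostomia symptom relief". The questionnaire is not named in that call, and nothing is said about pH.
- **Diary.** "Patients will be given a diary or questionnaire to record compliance to the product and Xerostomia symptom relief". The Xerostomia Questionnaire is listed as a separate measurement.

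**The concern.** Carry-forward acts in two ways on a change from baseline to week 12:

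- With a week-6 value, the subject's change becomes week 6 minus baseline, so anything that happens between weeks 6 and 12 is assumed away.
- With no follow-up value, the baseline is carried and the change is exactly zero.

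If the product works and its effect builds over time, both pull the estimated difference towards zero. If both arms improve over time and one arm loses more subjects, the zeros lower that arm's mean change and create a difference that does not exist. In either case the t-test counts the filled-in values as observations, so its standard error does not reflect what is unknown.

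The CPAP measures have downloads as a back-up; these two endpoints do not. Relief of dry mouth is the secondary objective and the route by which the product is meant to improve CPAP compliance, so a distorted xerostomia result would affect how the primary result is read.

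**Working it through.** **Inputs from the documents.** 1:1 allocation, 16 per arm; two-sided t-test at 0.10; 30 subjects plus 2 expected dropouts. The dropout step reproduces: 30 + 2 = 32, and 2/32 = 6.25%, or 1 of 16 per arm if evenly spread.

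**Inputs assumed.** The documents give no SD, expected effect, correlation or time course for either endpoint. Assumed below: correlation 0.6 between visits and, where a true effect exists, 0.5 SD at week 6 and 0.9 SD at week 12. Missingness is unrelated to outcome.

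**1. Attenuation with equal loss in both arms.** Let m be the share missing week 12, w the share of those with a week-6 value, and r the week-6 effect divided by the week-12 effect. The expected carry-forward estimate divided by the true difference is

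1 − m(1 − w·r)

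At the planned m = 0.0625:
- no week-6 values (w = 0): 1 − 0.0625 = 0.9375
- all have week 6 (w = 1), r = 0.5: 1 − 0.0625 × 0.5 = 0.969
- all have week 6, r = 1: 1.00

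So attenuation is between 0% and 6.25%.

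With w = 0.5 and r = 0.5/0.9 = 0.556, the factor 1 − w·r is 0.722. For a true 0.90 SD:

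| Missing per arm | Calculation | Estimate |
|---|---|---|
| 6.25% | 0.90 × (1 − 0.0625 × 0.722) | 0.86 SD |
| 15% | 0.90 × (1 − 0.15 × 0.722) | 0.80 SD |
| 25% | 0.90 × (1 − 0.25 × 0.722) | 0.74 SD |

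Simulation agrees. Power with a true 0.9 SD falls from 87.6% with nobody missing to 84.9% with one subject per arm missing both visits.

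**2. False positives with no true difference.** Both arms improve by 1 SD at week 12. Every subject with no follow-up contributes zero, so an arm with share m missing both visits has mean change 1 − m.

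- 25% versus 5%: 0.75 − 0.95 = −0.20 SD; simulated false-positive rate about 17%.
- Exactly the planned 2 dropouts, both in one arm, both missing both visits: 14/16 − 1 = −0.125 SD; about 11%.
- The same 2, with week 6 carried (0.55 SD improvement at week 6 assumed): 10.6%.
- One per arm, baseline carried: no bias; about 8%. The two zeros lie far from the other changes and inflate the variance, which makes the test conservative.

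If loss is instead random at 12.5% in one arm and none in the other (2 of 16 on average, sometimes more), the rate is about 13%.

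**3. Does dropping carry-forward help?** In the 25% versus 5% case, a baseline-adjusted analysis of the observed week-12 values has bias 0.00 SD and a false-positive rate of about 10%. It also has higher power than the carry-forward t-test, although part of that gain comes from adjusting for baseline. The full repeated-measures model was not simulated; this check covers its simplest version.

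**The case against.** The strongest case against is one of size. These are secondary endpoints in a declared pilot, and at the plan's own dropout the error is a few percentage points. The 17% figure needs about 4.8 subjects lost (16 × 0.25 + 16 × 0.05), 2.4 times the planned 2. It also needs all of them lost before week 6, mostly from one arm, with a large common improvement. That stands, and it limits the priority.

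Three stronger readings are tempting, and the documents do not support them:

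- **That every missing subject is scored as unchanged, or that week-6 data go unused.** Only subjects missing both follow-up visits get a zero change. Carry-forward uses the week-6 value of anyone who misses week 12. It is completers' week-6 data that play no part, and a baseline-to-week-12 endpoint is in itself a legitimate choice.
- **That NeutraSal will lose more subjects.** The Risk/Benefit section reports a salty taste and some burning, but the placebo is sodium chloride, and the same section says most Sjogren's patients liked the product. The direction of any unequal loss is uncertain.
- **That the questionnaire score is certainly lost at a missed visit.** The call and the diary do collect symptom relief, though not as the total score, and the data collection instruments are in the IRB submission, which is not among these documents. A phone form may exist there.

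The replacement also has limits. A model with baseline only as a covariate leaves out subjects with no follow-up, and any likelihood-based model relies on missingness at random, which is doubtful if intolerance or lack of relief drives dropout. These limits affect how the fix is specified; they do not make filled-in zeros preferable.

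**Conclusion.** The concern holds in this limited form. One unrestricted carry-forward rule fills in the week-12 xerostomia score and pH with the week-6 value or, failing that, the baseline, and the t-test treats the result as measured.

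With exactly the planned 2 of 32 dropouts, attenuation is 0–6% if losses are even, and false positives are about 8–11% against 10%. The problem becomes material with more or unequal loss: 0.74 instead of 0.90 SD at 25% missing, and about 17% false positives at 25% versus 5% missing both visits. All these sizes depend on the assumed correlation, effects and time course, and on missingness unrelated to outcome. Informative dropout could move the bias either way. Priority is low to moderate.

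**What to change.** - **Statistical Analysis Plan.** For the xerostomia score and salivary pH, replace carry-forward with a likelihood-based repeated-measures model: weeks 6 and 12 as outcomes, arm by visit, adjustment for baseline, the arm difference at week 12 as the contrast, and small-sample degrees of freedom such as Kenward-Roger. Enter baseline as a covariate or, to keep subjects with no follow-up in the model, as an outcome constrained to be equal across arms. State the missing-at-random assumption. Keep carry-forward only as a sensitivity analysis.
- **Follow Up Visits.** Name the full Xerostomia Questionnaire in the missed-visit phone call, unless the form in the IRB submission already includes it, and record the mode of administration. pH cannot be recovered by phone, so for that endpoint the model alone must deal with missing values.

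The cost is a few lines of text, one standard model on visits already scheduled, and a few minutes per call. The downsides are a possible phone-versus-clinic difference in the few subjects affected and a slightly more complex analysis than a t-test.

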NeutraSal is a powder in individual packets. Placebo is a powder in individual packets. NeutraSal and placebo are to be stored in a location with normal room temperature and avoidance of moisture.

Conflict of Interest:

There is no expected conflict of interest.

Publication and Presentation Plans:

Abstract presented as a poster or an oral presentation at upcoming national/international Pulmonary, Critical Care and Sleep meetings, dental meetings and possible publication.

STUDY SIGNIFICANCE:

Xerostomia is excessive dryness of the mouth. It is due to insufficient saliva secretion.

Xerostomia is often accompanied by buccal symptoms and signs such as impaired sense of taste, fetid breath and mouth ulcers, and it disturbs functions such as speech, chewing and swallowing. Because of reduced salivary secretion, there is disturbance of the microbial colonization of the buccal cavity, increased demineralization and decreased remineralization of the teeth, impaired retention of dentures, dehydration of the mucosa and reduced lubrication of the buccal mucosa. These complications may take the form of dental caries, candidiasis, atrophy and feelings of burning of the mucosa, difficulty retaining dentures, impaired speech and swallowing and impression of decreased or impaired sense of taste. Xerostomia has significant harmful effects on the buccal cavity and on the quality of life of patients.

Xerostomia is one of the major factors affecting compliance with cpap therapy.

Treatments of xerostomia are saliva substitutes and saliva stimulants. NeutraSal is a saliva substitute. Obstructive Sleep Apnea Syndrome (OSAS) is a common disorder with a prevalence of (defined in this study as an apnea-hypopnea index (AHI) of 5 or higher and excessive daytime sleepiness) to be 2% in women and 4% in men in the 30-60 year age group¹⁰. The estimated prevalence of an AHI of 5 or greater with no symptoms was even higher at 9% in women and 24% in men in the same age group. Thus OSAS is a major public health problem.

Common manifestations of OSAS include snoring, excessive daytime sleepiness and fatigue. In addition, emerging data has linked OSAS to neurocognitive deficits such as memory loss and attention deficits¹, hypertension, arrhythmias, coronary artery disease², congestive heart failure, stroke³ and insulin resistance⁴. Given the significant impact of OSAS on overall health and quality of life, it is very important to treat it optimally.

The treatment of OSAS most commonly involves the use of Continuous Positive Airway Pressure (CPAP) to maintain patency of the upper airway. CPAP being noninvasive and very effective at treating OSAS, is generally considered first line treatment for OSAS, in the absence of any contraindications to its use. CPAP machines blow mildly pressurized air into a connected tube and a mask or other attaching device that extends from the other end of the tube. This pressurized air gently opens the airways and keeps them open. Patient compliance with CPAP usage is often limited by mouth dryness which is a common side effect. This may be further exacerbated in patients who are mouth-breathers or have underlying conditions predisposing to Xerostomia. Heated humidification may have some effect on improving the mouth dryness but does not eliminate it entirely in most cases, thus decreasing patient adherence to CPAP therapy. Neutrasal is a supersaturated calcium phosphate rinse which has been shown to improve xerostomia in Sjogren's syndrome patients. Our study will attempt to show improvement in patient CPAP compliance, salivary parameters such as pH and salivary flow and overall quality of life with the use of NeutraSal, which will be used to prevent/treat the xerostomia associated with CPAP therapy.

References:

- 1 Verstraeten E. Neurocognitive effects of obstructive sleep apnea syndrome. *Curr Neurol Neurosci Rep* 2007; 7:161-166
